# **INTRACORPOREAL VS. EXTRACORPOREAL ANASTOMOSIS IN PATIENTS UNDERGOING LAPAROSCOPIC RIGHT HEMICOLECTOMY: A MULTICENTER RANDOMIZED CLINICAL TRIAL (THE IVEA-STUDY)**

## **INTRODUCTION AND JUSTIFICATION OF THE WORK:**

### **BACKGROUND AND CURRENT STATUS OF THE SUBJECT**

Colon cancer is the third most frequent malignant tumor currently constituting a major health problem in Western countries. In Spain, it represents approximately 15% of the incidence of all tumors, registering more than 25,000 new cases per year, and is the second cause of cancer death (more than 13,000 deaths / year).

The average survival in our country is 48% at 5 years after the diagnosis of colon cancer, possibly because it is performed late in most cases and because of the little introduction of screening programs for this neoplasm.

The objective of the surgical treatment of colon cancer is the block resection of the tumor with correct margins of safety, as well as the exeresis of all the corresponding lymph node territory with the ligation of the vessels at their origin. Usually, a proximal and distal margin of at least 5 cm is considered correct, although this is further determined by the vascularization of the colonic segment. When the colon has invaded the surrounding structures locally, a block resection should be scheduled.

Tumors located in the cecum or ascending colon require 5-10 cm of terminal ileum with ligation of the ileocolic pedicle and right branch of the middle colic vessels, with resection at the level of the middle transverse colon (right hemicolectomy). A tumor located at the hepatic angle or in the proximal transverse colon requires an enlarged right hemicolectomy, with ligation of the ileocolic artery, right colic and middle colic, and resection of the distal transverse or descending colon. Intestinal reconstruction is performed by a manual or mechanical ileocolic anastomosis. For years, multiple investigations have been realized to determine the best technique for ileocolic anastomosis (suture in one or two planes, simple or continuous suture, resorbable or non-absorbable material, mechanical sutures, etc.), but until now there have been no differences regarding the rate of suture dehiscence.

Lymphadenectomy has different objectives: staging the tumor in the surgical act and trying to perform a complete resection to improve oncological results, this way evaluating the quality of the surgical procedure. There is a direct correlation between the number of lymph nodes excised, and therefore evaluated, with survival. For a long time is known that the existence of ganglia in the surgical piece depends on the surgical technique and the methodology used. The Clinical Guidelines recommend a minimum of 12 lymph nodes studied for a correct tumor stage. For years, minimally invasive surgery is performed in a large number of interventions in a safe way. Jacobs et al described the first laparoscopic resection in sigma cancer in 1991. Since then the experience has grown rapidly, and different clinical trials showed improvements in the postoperative period of the patient without oncological differences. Only the Lacy study showed greater lymph node excision with the laparoscopic technique.

At present laparoscopic surgery has show to be a safe technique, which a better recovery of the patient (decreasing postoperative ileus, early oral diet, more controlled pain, fewer days of hospital stay ...) and also reduces the rates of complications if performed by experienced surgical teams. The most recent randomized studies have shown no oncological differences with respect to open surgery. The percentage of conversion in the literature varies from 2 to 46% depending mainly on the experience of the team.

Among surgical techniques by means of minimally invasive surgery, right colectomy can be considered a particular case in which the technical difficulty added by the frequent anatomical variations, especially vascular ones, have meant a more gradual acceptance of the laparoscopic approach. Unlike the technique used in rectal-sigmoid neoplasms, ileocolic anastomoses after right hemicolectomy can be performed in two ways: extracorporeal or intracorporeal.

The extracorporeal anastomosis is performed by externalizing the ileum and colon through the incision through which the surgical specimen is extracted. The intracorporeal anastomosis is performed completely laparoscopically, and the incision made is only to remove the surgical specimen.

## **JUSTIFICATION:**

Right hemicolectomy using a minimally invasive technique allows for an earlier recovery, with less postoperative pain and less hospital stay. After right hemicolectomy, the ileocolic anastomosis is not performed "naturally" as is habitually done in low anterior resections or sigmoidectomies. There is, therefore, no standardization in the reconstruction technique, with two possibilities: intracorporeal and extracorporeal anastomosis.

The intracorporeal anastomosis allows proper visualization of it, ensuring adequate conformation (absence of rotation or traction), in addition allowing the closure of the mesos and avoiding the possible appearance of internal hernia, also allowing to choose the location and length of the incision necessary for the extraction of the piece. On the other hand, it is a difficult technique that requires high training in advanced laparoscopy.

The extracorporeal anastomosis is performed by extracting both ends (terminal ileum and transverse colon) through the incision through which the piece is obtained, and the anastomosis is performed. It does not require, therefore, an important training in intracorporeal sutures. On the contrary, it forces to make the abdominal incision in the area that allows the extraction of said ends. In obese patients it can be difficult since the mesos are short and do not allow their extraction easily, so sometimes, it forces excessive traction. In addition, intestinal rotations during the anastomosis may go unnoticed.

Although there are currently defenders of both techniques, the extracorporeal anastomosis is currently the most performed in our environment and will be used as a reference treatment in the present study.

Numerous studies have been published comparing both techniques. A very recent meta-analysis, including 12 non-randomized comparative studies with 1492 patients, concluded that intracorporeal anastomosis is associated with less morbidity and a reduction in hospital stay, suggesting a faster recovery. To date, no well-designed, prospective, randomized and randomized study exists in the literature. We believe it is necessary, therefore, to carry out a project that compares both surgical techniques in the treatment of right colon cancer and assess which is associated with a lower postoperative morbidity.

## **OBJECTIVES:**

The objectives of our study are:

### **GENERAL:**

- To compare perioperative morbidity between laparoscopic right hemicolectomy with intracorporeal anastomosis versus extracorporeal anastomosis within 30 days after surgery.

## SPECIFIC:

- Quantify, by means of the Visual-Analogue Scale (VAS), postoperative pain 24 hours after surgery and the day of hospital discharge, and determine which of the two laparoscopic right hemicolectomy techniques produces less pain.
- To evaluate and compare the rate of anastomotic dehiscence in both groups of anastomoses up to 30 days after surgery.
- To evaluate the difference in surgical time between right hemicolectomy with intracorporeal versus extracorporeal anastomosis.
- To evaluate the infection rate of the surgical site in both groups up to 30 days after surgery.
- To compare the difference of days of hospital stay in both groups of anastomoses.

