### **Outcome Measures**

Patient baseline characteristics at the time of surgery; age, gender, ASA score, major comorbidities and operative variables were obtained from each patient. The 30-day postoperative complications were recorded. Complications were defined as any deviation from the normal postoperative course and graded using Clavien-Dindo classification. The term anastomotic leakage (AL) defines all conditions with clinical or radiologic anastomotic dehiscence, with or without the need of surgical revision. Wound infection was defined as spontaneous drainage of purulent material from the wound or from the surgeon's deliberate revision and a positive culture of drained serous fluid. The length of hospital stay (LOS), reinterventions, postoperative pain according to the visual analogical scale were also documented. For the subsequent analysis of the patient, the conversion to an extracorporeal anastomosis among the totally laparoscopic procedures or conversion to open surgery has not been included.

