**Postoperative Management**

After surgery, nasogastric tubes were not used, the urinary catheters were removed on postoperative day 1. Early mobilisation was practised and oral fluids administered early, switched to a diet after first passage of flatus. and endovenous hydrations were suspended. Criteria for discharge included pain control, absence of nausea and tolerance of a soft diet without restrictions and passage of gas and stool. All patients were followed-up for at 30 days.

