### **CHRONOGRAM-PHASES OF WORK:**

- **SURGICAL INTERVENTION:** We will perform surgical interventions throughout the first 18 months of the study. Patients will be randomized and, depending on the group, the technique will be performed by intra-or extracorporeal anastomosis. During the first eighteen months.
- **FOLLOW UP:** Patients will be assessed daily during their hospital stay, and subsequently in consultation according to the protocol that is attached in methodology.
- **DATA COLLECTION:** All data will be included in the data collection notebook, and will be added in a Microsoft Access XP database, throughout the entire study.
- **STATISTICAL STUDY:** Once all the data have been collected, a statistical study will be carried out using the SPSS program as described in the data analysis (methodology). One month
- **REDACTION OF RESULTS.** The results will be written when the definitive statistical study is carried out according to: introduction, objectives, hypothesis, patients and methods, results, discussion, conclusions and bibliography. Five months.

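### Discharge-day pain is read at a time that can differ by arm, so it should not help decide which technique hurts less

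*Protocol*

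**What the plan says.** The first of the five specific objectives in the Protocol is to quantify "postoperative pain 24 hours after surgery and the day of hospital discharge" on a visual analogue scale and to "determine which of the two laparoscopic right hemicolectomy techniques produces less pain". Both readings therefore feed a between-arm conclusion.

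Three other statements bear on the second reading:

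- Postoperative Management: "Criteria for discharge included pain control, absence of nausea and tolerance of a soft diet without restrictions and passage of gas and stool".
- Specific objectives, last item: "To compare the difference of days of hospital stay in both groups of anastomoses".
- Justification: a meta-analysis of non-randomized studies "concluded that intracorporeal anastomosis is associated with less morbidity and a reduction in hospital stay".

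Outcome Measures adds only that "postoperative pain according to the visual analogical scale were also documented", without a time. The chronogram states that "Patients will be assessed daily during their hospital stay"; this is a daily assessment, not a daily VAS.

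**The concern.** Randomization protects a comparison made at the same time after surgery in both arms. The day of discharge is an outcome of treatment, and it departs from a fixed time in two separate ways.

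1. **Selection on pain.** Patients leave once pain is judged controlled, so discharge-day readings lean towards low values in both arms. The arm with more pain can reach that state later, and a true difference shrinks.
2. **Different days.** If intracorporeal patients go home sooner for any reason, such as earlier bowel function, they are read earlier on a falling pain curve. This shrinks a true benefit or, where pain is equal, makes the intracorporeal arm look more painful. It needs no pain criterion. A pain criterion partly offsets it, because it caps what can be recorded.

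A statement about which technique hurts less could thus reflect when patients went home. The discharge-day result could also disagree with the 24 h result for reasons unrelated to pain.

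**Working it through.** **No figure to reproduce.** The Protocol gives no VAS mean, SD, cut-off, pain curve or expected stay difference. The only document figure used is 75 patients per group (Sample Size Calculation). Every other input below is an assumption.

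**Model A (linear decline).** 400,000 simulated patients per arm.

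- Daily VAS = patient level at 24 h (mean 4.5, SD 1.5) − 0.6 per day + noise (SD 0.7), clipped to 0–10.
- Bowel-recovery day: mean 4.5, SD 1.3.
- Discharge: first day on or after bowel recovery with VAS at or below a cut-off of 2, 3, 4 or 5, or with no cut-off.

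Differences are extracorporeal minus intracorporeal; a positive value means less pain with intracorporeal. Recovery gaps are in favour of intracorporeal.

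| Truth | Cut-off 2 | 3 | 4 | 5 | None | Fixed time |
|---|---|---|---|---|---|---|
| Benefit 1.0, equal recovery | 0.25 | 0.46 | 0.63 | 0.73 | 0.80 | 0.98 at 48 h |
| Benefit 1.0, recovery 1 day earlier | 0.09 | 0.18 | 0.25 | 0.30 | 0.34 | 0.98 at 48 h |
| No difference, recovery 1 day earlier | −0.12 | −0.23 | −0.35 | −0.45 | −0.54 | 0.00 at 24 h and 48 h |

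**Hand check of the last simulated column.** With no cut-off, and ignoring the floor of the scale, the apparent difference is the true difference minus (daily decline × recovery gap):

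- Benefit 1.0, one day: 1.0 − 0.6 × 1 = 0.40 (simulated 0.34).
- No difference, one day: 0 − 0.6 × 1 = −0.60 (simulated −0.54).
- No difference, half a day: 0 − 0.6 × 0.5 = −0.30 (simulated −0.27; −0.06 to −0.27 over all cut-offs).

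The floor accounts for the remainder. A tighter cut-off makes the false difference smaller but shrinks a true one more.

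**Consequences for a test.** Normal approximation, 75 per arm, two-sided 0.05 (assumed), with d the simulated difference and s₁, s₂ the simulated SDs:

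SE = √[(s₁² + s₂²)/75]; probability of significance = Φ(|d|/SE − 1.96) + Φ(−|d|/SE − 1.96).

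- Benefit 1.0, equal recovery: power 62% to 89%.
- Benefit 1.0, recovery one day earlier: 13% to 25%.
- Benefit 1.0, read at 48 h: 96%.
- No difference, recovery one day earlier: falsely significant in 20% to 50% of trials (about 20% to 47% for cut-offs 2 to 5), against a nominal 5%.
- No difference, half a day earlier: about 9% to 17%.

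**Sensitivity to the decline (cut-off 3; 0.3 / 0.9 per day).** Benefit with equal recovery: 0.38 / 0.39. Benefit with recovery one day earlier: 0.25 / 0.04. No difference, recovery one day earlier: −0.08 / −0.37.

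**Model B (exponential decline).** VAS falls at 0.25 per day, cut-off 3, recovery gap 1.5 days where there is one, same sign convention.

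| Truth | 24 h | Fixed day 4 | Discharge day |
|---|---|---|---|
| Equal pain, earlier recovery | 0.00 | 0.00 | −0.34 |
| Benefit 1.0 at 24 h, equal recovery | 0.99 | 0.46 | 0.23 |
| Benefit 1.0 at 24 h, earlier recovery | 0.98 | 0.46 | −0.12 |

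Both models shift the discharge-day comparison against the arm that leaves earlier. They differ on whether a true benefit changes sign. With a constant gap and no cut-off, reversal needs a recovery gap above about 1.0/0.6 ≈ 1.7 days. In Model B the true gap has already waned to 0.46 by day 4, so 1.5 days is enough.

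**The case against.** **The passages do not contradict one another, and pain on going home is a meaningful quantity.** This is true. The difficulty is using it to rank the techniques. As a description of patients on leaving hospital it is sound.

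**Handling of the differing day could sit in a statistical analysis plan that is not at hand.** Accepted: the silence of the Statistical Analyses section carries no weight here. The objective itself, however, fixes the two time points and the conclusion drawn from them.

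**The sizes are assumed, and the headline rate uses the larger gap.** This also stands. The Protocol cites only a direction for stay, from non-randomized studies. The 20% to 50% needs a full one-day gap, and the 50% end needs no pain cut-off, although pain control is a stated criterion. Some figures move with how the recovery day is rounded: with nearest-day rounding, the lowest equal-recovery power is 55% rather than 62%.

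**48 h flatters the fixed-time alternative.** This is partly right. In Model A a fixed day 5 gives about 0.83, so 0.98 − 0.83 = 0.15 of the equal-recovery loss comes from reading later, near the floor. Against day 5, the further loss is 0.83 − 0.25 = 0.58 at cut-off 2, 0.37 at 3, 0.20 at 4, 0.10 at 5 and 0.03 with none. Lateness therefore explains much of the loss at loose cut-offs and little at tight ones. It does not explain the false difference when pain is equal, since a fixed day returns 0.00.

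**The remedy may come too late.** Much of the methods text is in the past tense, so a new reading may be impossible. The conclusion can still rest on 24 h alone.

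**Conclusion.** The concern holds. The objective rests part of a between-arm pain conclusion on a reading whose timing depends on outcome, and the Protocol itself supplies both conditions: pain control as a discharge criterion, and a stay expected to be shorter with intracorporeal anastomosis.

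The firm part is the direction. If the intracorporeal arm leaves earlier while pain is still falling, the discharge-day comparison moves against it, and selection on pain control shrinks a true difference. The size is not known. It depends on the assumed pain curve, variability, recovery gap and cut-off, and the sign under a true benefit depends on the model.

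The reach is limited to one of two time points in one of five specific objectives. The 24 h comparison, the primary endpoint and the sample size are untouched. The change is worth making because it removes an avoidable bias at very little cost.

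**What to change.** Reword the pain objective so that the between-arm conclusion rests on fixed times: VAS at 24 h and, where it can still be collected, one further fixed early inpatient reading, for example at 48 h, taken at the daily assessment. If a second reading can no longer be collected, use 24 h alone. Report discharge-day VAS descriptively by arm, beside the day of discharge, with no between-arm test or conclusion. The discharge criteria are not in question.

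**Cost.** A one-line change to the objective and, if the second reading is added, one more entry in the data collection notebook. State how patients already discharged at 48 h are handled. In Model A they are at most 2.7%, or up to about 6% with nearest-day rounding. Making discharge-day VAS descriptive needs no new data, but if data already exist the change should be dated and justified without knowledge of results by arm.

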## **WORK HYPOTHESIS:**

In patients with right colon cancer, laparoscopic right hemicolectomy with intracorporeal anastomosis presents less perioperative morbidity than extracorporeal anastomosis.

## **MATERIALS AND METHODS:**

Patients treated in 4 Spanish South-east hospitals with preoperative diagnosis of right colon neoplasm were included. All participating hospitals have vast experience in minimally invasive approach.

### **Study Design**

The IVEA-study is a prospective multicenter randomized trial with two parallel groups being done IA or EA in laparoscopic right hemicolectomy for right colon neoplasia. The patients were randomized using <http://www.randomization.com>.

### **Inclusion and Exclusion Criteria**

- Inclusion criteria. All patients had to be 18 years of age or over, to be programmed for laparoscopic surgery for right colon neoplasm and provide a signed written consent form.
- Exclusion criteria. All patients who do not meet all the inclusion criteria were excluded. The other exclusion criteria included the need for emergency surgery, renal failure defined by haemodialysis, Crohn's disease, ulcerative colitis, T4 tumor invading adjacent organs, synchronous colorectal neoplasm, metastasis or carcinomatosis at diagnosis, bowel obstruction, psychiatric disorders or contraindication for laparoscopic approach.

### **Outcome Measures**

Patient baseline characteristics at the time of surgery; age, gender, ASA score, major comorbidities and operative variables were obtained from each patient. The 30-day postoperative complications were recorded. Complications were defined as any deviation from the normal postoperative course and graded using Clavien-Dindo classification. The term anastomotic leakage (AL) defines all conditions with clinical or radiologic anastomotic dehiscence, with or without the need of surgical revision. Wound infection was defined as spontaneous drainage of purulent material from the wound or from the surgeon's deliberate revision and a positive culture of drained serous fluid. The length of hospital stay (LOS), reinterventions, postoperative pain according to the visual analogical scale were also documented. For the subsequent analysis of the patient, the conversion to an extracorporeal anastomosis among the totally laparoscopic procedures or conversion to open surgery has not been included.

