### **Surgical technique**

Perioperative care was identical for both groups. Bowel preparation was not used, and intravenous antibiotics were administered preoperatively. Under general anesthesia, the patients were placed supine on the operating table, with open legs. Urinary catheter was inserted. Pneumoperitoneum was induced using carbon dioxide insufflated to an average pressure of 12 mmHg by placement of a infraumbilical trocar. Three additional ports were inserted: 12 mm in the left lower quadrant and two 5-mm trocars in the right lower quadrant and upper left quadrant. Laparoscopic right colectomy was performed with a medial-to-lateral approach, starting with ligation of the blood vessels at their origin followed by mobilization of the bowel and lateral

dissection of the terminal ileum and colon attachments. The colon and ileum were transected with a 60-mm laparoscopic stapler in that order, followed by an ileo-transverse anastomosis.

• **Intracorporeal anastomosis:**

The specimen was preferentially extracted via a small Pfannenstiel-type incision with the protection of an Alexis Wound Protector (Applied Medical, Rancho Santa Margarita, California, USA). The incision for the extraction of the right colon is sutured in two layers by absorbable suture. The ileum was held by the assistant to prevent rotation of its mesentery. A stay suture was applied 10 cm proximal and distal to the stapled ends of the terminal ileum and colon, respectively, and then held by the assistant. An enterotomy and colotomy were made sharply at the antimesenteric corner of the staple lines. An isoperistaltic side-to-side anastomosis was fashioned with a 60-mm laparoscopic stapler. A 2-0 double-barbed suture was used to close the enterocolotomy, in two planes (the first submucosal, and the second sero-serous). The mesenteric defect and the mesocolon after the construction of either type of anastomosis were not closed. Drains were not used routinely.

• **Extracorporeal anastomosis**

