The mobilized colon was externalized preferentially via a transverse or midline incision with the protection of an Alexis Wound Protector (Applied Medical, Rancho Santa Margarita, California, USA). A stay suture was applied 10 cm proximal and distal to the stapled ends of the terminal ileum and colon. An enterotomy and colotomy were made sharply at the antimesenteric corner of the staple lines. An isoperistaltic side-to-side anastomosis was fashioned with a 60-mm laparoscopic stapler. A 2-0 double-barbed suture was used to close the enterocolotomy, in two planes (the first submucosal, and the second sero-serous). The mesenteric defect and the mesocolon after the construction of either type of anastomosis were not closed. The incision for the extraction of the right colon and the realization of the anastomosis is sutured in two layers by absorbable suture. Drains were not used routinely.

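### Does a wound infection definition fail the objective on surgical-site infection?

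*Protocol*

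**What the plan says.** The protocol's list of specific objectives has one item on infection: "To evaluate the infection rate of the surgical site in both groups up to 30 days after surgery". A separate item covers the anastomosis: "To evaluate and compare the rate of anastomotic dehiscence in both groups of anastomoses up to 30 days after surgery".

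The Outcome Measures section supplies the definitions. For infection there is only this: "Wound infection was defined as spontaneous drainage of purulent material from the wound or from the surgeon's deliberate revision". The sentence then adds a positive culture of drained serous fluid. Leakage has its own definition: "The term anastomotic leakage (AL) defines all conditions with clinical or radiologic anastomotic dehiscence, with or without the need of surgical revision". A general rule covers everything else: "Complications were defined as any deviation from the normal postoperative course and graded using Clavien-Dindo classification". Complications are recorded for 30 days.

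Outcome Measures does not use the term surgical site, and no section divides infections into incisional and deeper types.

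**The concern.** The objective and the definition use different words, and the difference could matter. Many readers would take surgical-site infection to include an abscess or collection inside the abdomen as well as an infected incision. The wound criterion looks only at the wound. On that reading, an intra-abdominal infection with dehiscence counts as leakage. One without dehiscence appears only as a graded complication within overall morbidity. A published surgical-site infection rate would then be a wound infection rate under a wider name.

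The comparison makes this more than pedantry, because the arms differ at the wound. In the intracorporeal arm, "The specimen was preferentially extracted via a small Pfannenstiel-type incision". In the extracorporeal arm, "The mobilized colon was externalized preferentially via a transverse or midline incision". They also differ in where the bowel is joined: "The extracorporeal anastomosis is performed by externalizing the ileum and colon through the incision through which the surgical specimen is extracted", whereas the intracorporeal join is made inside the abdomen. Wound and intra-abdominal infection could therefore respond differently to the technique, and a wound-only rate could not show it.

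**Working it through.** The protocol states no infection rate or infection effect size, so there is no figure to reproduce. The check is a comparison of texts, followed by some arithmetic on scale.

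**1. Do the objectives map onto the outcomes?**

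| Specific objective | Counterpart in Outcome Measures |
|---|---|
| Pain by visual analogue scale | Postoperative pain on that scale |
| Anastomotic dehiscence | Anastomotic leakage, defined through dehiscence |
| Surgical time | Operative variables |
| Infection of the surgical site | Wound infection |
| Hospital stay | Length of stay |

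Each objective has one counterpart. The infection row is the only one where neither text uses the other's key term, but no other definition competes for the place.

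**2. Where does each event go under the wound criterion?**

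- Wound infection: infection rate and overall morbidity.
- Intra-abdominal infection with dehiscence: leakage rate and overall morbidity.
- Intra-abdominal infection without dehiscence: overall morbidity only.
- Wound and intra-abdominal infection in the same patient: still counted once in the infection rate.

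No event drops out of the primary endpoint. Only the third group is absent from both specific rates.

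**3. What does one such patient weigh?**

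The Sample Size Calculation section gives 75 per group, or 84 after allowing for drop-out. One patient is 100/75 = 1.33 percentage points of an arm's rate, or 100/84 = 1.19. If x patients are left out in the extracorporeal arm and y in the intracorporeal arm, the difference in rates shifts by (x − y)/75. With x = y the shift is zero. The protocol gives no basis for x or y.

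**4. Can the planning rates bound the relative loss?**

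The planned complication rates are 30% and 11%. At 75 per group the expected numbers of patients with any complication are 0.30 × 75 = 22.5 and 0.11 × 75 = 8.25. Infected patients are a subset, so it is tempting to say that one omitted patient is no less than 1/22.5 = 4.4% or 1/8.25 = 12.1% of an arm's infected patients. That is not a bound, because 22.5 and 8.25 are expectations and not ceilings. If 9 intracorporeal patients had a complication and all 9 were infected, one would be 1/9 = 11.1%, already below 12.1%. These percentages should not be relied on.

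**The case for a change.** The strongest case for a change is that the mismatch lies inside the protocol. The protocol names the objective and also writes the definitions, so the gap cannot simply be left to an analysis plan. Two careful readers could count different events: one only wound events, the other also an abscess. The dehiscence objective is tied to its definition by a shared word and the infection objective is not. The remedy would be one sentence.

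Much of this stands. The link is unstated, and a wound-only rate supports a conclusion about wounds only. Two things weaken the case for a required change. First, the charge that deeper infections are wrongly left out relies on a classification that the protocol does not use; from the text alone, one can say only that two terms are not joined. Second, the obvious remedy, a composite of wound and deeper infection with leak-related cases counted under both infection and dehiscence, is a preference. It would make two outcomes overlap that the objectives keep apart. Nor is it certain to be free: complications are recorded and graded, but the protocol does not show that the data collection notebook captures the site of an infection.

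**Conclusion.** No change to the plan is called for. This is loose terminology in one secondary objective. The natural pairing of the single infection objective with the single infection definition gives a usable, clearly defined rate. Leakage is measured separately, remaining infections stay within the recorded 30-day complications, and the primary comparison of overall morbidity does not depend on the answer.

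The effect on the secondary result cannot be sized from the protocol. The only firm figure is 1.33 percentage points of an arm's rate per reclassified patient at 75 per group, with no effect on the difference if both arms lose equally many. Whether the arms would differ in intra-abdominal infection without a leak is unknown.

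This conclusion assumes that the wound criterion is the intended measure and that the report describes the result as wound infection. If the investigators meant something wider, they should say which further recorded infections they counted. That is a matter of labelling and exposes no stated rule that would give a wrong result.

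### The wound-infection definition does not fix how its 'or' and 'and' group, so the same wound can be scored either way in the secondary 30-day infection outcome

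*Protocol*

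**What the plan says.** The Protocol, under Outcome Measures, gives one case definition for wound infection: "spontaneous drainage of purulent material from the wound or from the surgeon's deliberate revision and a positive culture of drained serous fluid". It is the only infection definition in the document.

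It serves a named specific objective: "To evaluate the infection rate of the surgical site in both groups up to 30 days after surgery".

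Several centres apply it: "Patients treated in 4 Spanish South-east hospitals with preoperative diagnosis of right colon neoplasm were included".

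The primary outcome rests on a different and broader rule in the same section: "Complications were defined as any deviation from the normal postoperative course and graded using Clavien-Dindo classification".

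The Protocol describes no adjudication of infections and does not say which of the wound-infection elements need a culture.

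**The concern.** The sentence joins its elements first with 'or' and then with 'and', with no punctuation or numbering to show what the culture condition attaches to. It could qualify only the wounds that the surgeon opens, qualify every wound, or stand as a further criterion of its own. These are different rules, and they disagree on ordinary presentations. The plainest case is a wound that the surgeon opens and finds to contain pus.

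At stake is the consistency of the infection rate that the trial sets out to compare. The extraction incision differs by arm (preferentially Pfannenstiel for the intracorporeal technique, transverse or midline for the extracorporeal one), so wound infection is an outcome on which readers will look for a difference. A case count that depends on how each site parses one sentence is a weak basis for that comparison.

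**Working it through.** The plan states no figure on this point, so there is none to reproduce. The check is a truth table of the sentence, followed by the weight of one case.

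**Elements**
- S: spontaneous purulent drainage
- R: deliberate opening by the surgeon
- P: pus found at that opening
- C: positive culture of drained serous fluid

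**Readings**
- A, culture tied to opening only: S or (R and C)
- B, culture tied to both sources of pus: (S or (R and P)) and C
- List, 'and' meaning 'as well as': S or (R and P) or C

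| Presentation | A | B | List |
|---|---|---|---|
| Spontaneous pus, no positive culture | yes | **no** | yes |
| Spontaneous pus, positive serous culture | yes | yes | yes |
| Pus at opening, no positive serous culture | **no** | **no** | yes |
| Pus at opening, positive serous culture | yes | yes | yes |
| Opened, no pus, positive serous culture | yes | **no** | yes |
| Opened, no pus, no positive culture | no | no | no |
| Not opened, no pus, positive serous culture | no | no | yes |

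The results are as follows.

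1. Pus at opening without a positive serous-fluid culture is not an infection on A or B, the two groupings that keep 'and' as a logical AND. It counts only on the list reading.
2. Spontaneous pus without a positive culture is also lost on B. So is an opened, culture-positive wound without pus.
3. A variant of B, (S or R) and C, recovers the opened, culture-positive wound. It still loses both kinds of pus when no culture is positive.
4. The readings agree on pus with a positive serous culture, and on an opened wound with neither pus nor a positive culture.

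**Weight of one case.** Sample Size Calculation gives 84 patients per group to be included and 75 before the drop-out allowance.
- 1/84 = 0.0119, or 1.2 points
- 1/75 = 0.0133, or 1.3 points

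The Protocol gives no expected infection rate, no share of wounds that are opened and no culture practice. The number of wounds that would change category therefore cannot be estimated from it.

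**The case against.** The strongest reply is that a clinician would read the sentence sensibly. The repeated 'from' ties both sources to purulent material, which favours counting pus found at revision. Reading B asks for pus and serous fluid in the same wound, which is close to self-contradictory. The list reading gives what was probably intended. This stands in part: a reader might infer that the definition simply excludes pus found at opening, and the text does not support that. The exclusion depends on taking 'and' as a logical AND and on the culture not being positive. What remains is that nothing in the Protocol tells a site to adopt the list reading, and a case definition should not rely on each site guessing the intent.

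Three stronger inferences are also tempting and are not supported.
- *The primary endpoint is compromised.* It is not, on the text. A purulent wound that the surgeon opens is a departure from the normal postoperative course, so the primary 30-day morbidity count should include it whatever the infection sentence means.
- *The comparison is biased between arms.* One definition applies to both arms, and nothing shows that misclassification would differ between them. The surgeon who decides whether to open and culture a wound may know the technique used, but that is a possible route to bias and not evidence of one.
- *The hospitals counted differently.* That four centres might do so follows from the wording. The document does not show that they did.

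It could also be said that an analysis plan not seen here may settle the matter. The Protocol has already fixed this definition itself, so the point concerns what is stated and not a detail left for later.

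**Conclusion.** The point holds as an ambiguity with a real consequence. On both groupings that keep 'and' as a logical AND, pus at deliberate opening is not an infection unless serous fluid also grows an organism. On one of them, spontaneous pus without a positive culture does not count either. The same wound can therefore be scored differently from site to site.

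The consequence is limited to the secondary 30-day surgical-site infection outcome. Its size can be given only per case: 1.2 to 1.3 points of one arm's rate for each reclassified wound, assuming the planned 75 to 84 patients per group. Any statement of how far the recorded rate would fall would rest on an invented infection count and an invented share of affected wounds, so none is offered. Because the correction is nearly free and the outcome is a named objective, it should be made.

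**What to change.** Replace the sentence in Outcome Measures, and the matching case report form entry, with separate alternatives, any one of which is sufficient:

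> Wound infection is either of: (a) purulent drainage from the incision, spontaneous or on deliberate opening, with or without culture; (b) a positive culture of non-purulent fluid from an incision the surgeon has opened.

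This settles every row of the table on which the readings disagree. Pus counts however it is found, and a positive culture of non-purulent fluid counts only when the incision was opened. It changes how an outcome is scored and not how patients are treated.

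The Protocol is written partly in the past tense, so some wounds may already be recorded. Those should be re-scored by someone unaware of the arm, only where the notes describe the drainage. The report should state how many wounds could not be re-scored.

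The cost is one sentence, one form entry and some review of notes. The small downside is that slightly more wounds may be counted.
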